The optimal management of type 2 diabetes (T2D) requires timely intensification of treatment to achieve and maintain target HbA1c, and prevent serious long-term complications (1, 2). Insulin therapy is the most efficacious diabetes treatment and T2D management guidelines recommended early consideration of insulin initiation (3, 4). However, international research suggests routine delay of clinically indicated insulin initiation among people with T2D (5, 6). Reasons for the perilous delay of treatment intensification are multifaceted, and include the experience of psychological insulin resistance (PIR) among people with T2D (7, 8). PIR is the reluctance to commence, use as recommended, or intensify insulin therapy (9). It is based upon the person's negative beliefs about insulin therapy, i.e. worries and inaccurate/unhelpful beliefs about the necessity for insulin, its side effects, its physical and social impact, and what insulin symbolises about their health and identity. Our research shows that one quarter of adults with T2D, for whom insulin is clinically indicated, are not at all willing to commence insulin if recommended by their health professional (10), and this 'willingness' is associated with actual insulin uptake (8).

Few evidence-based interventions exist to promote receptiveness to insulin therapy (11, 12), and none have been developed, evaluated, or are available, within Australia. Online interventions provide the ideal platform for wide reach (13), with minimal burden on limited healthcare resources. We have identified the need for a psycho-educational resource for people with T2D facing the decision to begin insulin therapy, which: a) is delivered online to enable wide reach with no additional burden on health service resources; b) recognises salient psychological barriers to insulin therapy among Australians with T2D (10, 14), c) utilises relevant, effective behaviour change techniques (15); d) is designed and refined with active involvement from end users, and; e) is rigorously evaluated to assess its impact on attitudes about insulin therapy. We will undertake a 24-month program of research to develop, pilot, and test the efficacy of a novel psycho-educational web-based resource to reduce negative attitudes towards insulin among adults with non-insulin using treated T2D. This stage-specific protocol describes the acceptability and feasibility testing of the intervention and the study design (pilot study).

1. ADMINISTRATIVE INFORMATION

1.1. Trial registration

The pilot study (Stage 2) will be registered on the Australian New Zealand Clinical Trials Registry (http://www.anzctr.org.au/) prior to commencement.

2. INTRODUCTION AND BACKGROUND

2.1. Background and rationale

Type 2 diabetes (T2D) is the fastest growing chronic condition in Australia (16), currently affecting 1.1 million Australians (17). T2D is a progressive condition that requires timely intensification of treatment to achieve and maintain optimal HbA1c (a measure of average blood glucose over 8-12

weeks), in order to prevent or delay the onset of devastating complications (e.g. kidney failure, blindness) (1, 2). A staged approach to pharmacological management of glucose levels in T2D is recommended (3, 18). First and second line therapies typically involve the introduction and intensification of oral hypoglycaemic agents (OHAs), while third line therapy and beyond may include the initiation of injectable treatments, including insulin therapy.

Insulin therapy is the most efficacious diabetes treatment available. It is the only diabetes management option that can maintain optimal blood glucose levels throughout the progression of beta cell failure (19). Complete beta cell failure generally occurs within 10 years of onset of T2D for most individuals (20). By preventing the development or progression of complications, insulin use indirectly contributes to maintaining both quantity and quality of life (21) and reduces the overall cost of diabetes, which are doubled in the presence of complications (22). Early consideration of insulin initiation is recommended internationally in T2D management guidelines (3, 4).

Despite proven efficacy, insulin is not used as widely as clinically indicated. In Australian primary care, ~50% of adults with T2D have an HbA1c above recommended target (>7%) (23, 24), suggesting many would benefit from optimised pharmacological treatment. However, only 20% of all Australians with T2D are using insulin (25), and research suggests insulin intensification is routinely delayed (6), typically occurring after several years of suboptimal Hba1c and maximum dose OHAS. For example, in the Australian 'Fremantle Diabetes Study', transition to insulin occurred at a median diabetes duration of 8 years and a median HbA1c of 9.4% (79mmol/mol) (26). This is corroborated by more recent data indicating that just 22% of adults with T2D for whom insulin was clinically indicated, receiving usual care in Victorian general practice, initiated insulin within the 12-month study period (27).

Reasons for the perilous delay of treatment intensification are multifaceted. Health professionals report personal barriers (e.g. lack of skills, experience, confidence) and systemic barriers (e.g. limited time and resources) to timely treatment intensification (7). Our research has demonstrated that insulin-specific health professional training programs and multi-disciplinary healthcare team support can facilitate timely insulin initiation (28). However, we have also demonstrated that willingness to commence insulin therapy among people with T2D is a predictor of actual insulin uptake independent of the model of care, or other clinical characteristics (8). One quarter of Australian adults with T2D, for whom insulin is clinically indicated, are 'not at all willing' to initiate insulin if recommended, and this group is significantly less likely to initiate insulin treatment (8). This suggests

that in addition to interventions to reduce health professional 'clinical inertia' (29), interventions are also needed that directly target people with T2D and address their psychological barriers to insulin use.

Psychological insulin resistance (PIR) is the reluctance to commence, use as recommended, or intensify insulin therapy experienced by a person with T2D (9). It is based upon the person's emotional and cognitive barriers to insulin use, e.g. worries about the necessity of insulin, its side effects, its physical and social impact, and feelings of guilt and self-blame about what insulin symbolises about health, self-care and identity. The latter includes the belief that insulin is an end-stage or 'last resort' treatment. Our research has previously identified that 80% of Australian adults with non-insulin-treated T2D believe that requiring insulin therapy means diabetes has become much more serious and 58% believe that insulin is a punishment or consequence of 'failing' to self-manage their diabetes previously (30). These negative beliefs and attitudes are significantly associated with low intention to initiate, and actual uptake of, insulin treatment (10, 31).

Negative attitudes toward, and reluctance to initiate, insulin treatment are malleable (8, 31, 32). However, despite the established relationship between belief/affects and treatment intensification, few interventions targeting negative attitudes toward insulin have been developed and none has been adequately evaluated, or implemented beyond trials (11, 12). Further, clinic-based interventions have been found to place additional burden on health professional resources (12). This suggests that an intervention to reduce negative attitudes towards insulin may be more accessible and acceptable if provided outside of, but complementary to, clinical care.

Online interventions provide the ideal platform for wide reach, with minimal burden on limited healthcare resources. Given the sheer size of the Australian population with T2D, the scalability of an intervention is an important consideration. The internet is a frequently used source of health information outside of, and between, medical appointments. In Australia, 86% of households have access to the internet (33), and one third of Australians with T2D and suboptimal HbA1c report seeking diabetes information online in the past 12 months (34). Internet-based interventions enable the cost-effective administration of highly accessible specialist behaviour change programs that can utilise content tailored to user characteristics, including interactive exercises (with immediate feedback), animations and audio/video resources. Compared to printed materials, internet-based interventions have been shown to be particularly beneficial for increasing engagement and comprehension among people with low health literacy, thus ensuring broad applicability (13).

Online interventions for the management of T2D with clear theoretical groundings and based on proven behaviour change techniques show favourable outcomes (35). Peak bodies (e.g. Diabetes Australia) publish resources online about T2D treatments. However, these materials are not theoretically informed, do not use evidence-based behaviour change techniques (15, 36), and are rarely developed in consultation with, or evaluated by, people with T2D. Furthermore, these materials focus on providing information that is physiological (e.g. treatment types and mode of action) and practical (e.g. injection techniques), with little or no content addressing important psychological barriers to injectable treatments. Therefore, it is unknown whether these resources are relevant or acceptable to users, and it seems unlikely that they would reduce psychological barriers to insulin use.

We have identified the need for a psycho-educational resource for people with T2D facing the decision to begin insulin therapy, which: a) is delivered online to enable wide reach with no additional burden on health service resources; b) recognises salient psychological barriers to insulin therapy held by Australians with T2D (10, 14, 30), c) utilises relevant, effective behaviour change techniques (15, 36); d) is designed and refined with active involvement from end users (people with T2D) to ensure content is relevant and acceptable, and; e) is rigorously evaluated to assess its impact on attitudes to insulin therapy.

We will undertake a 24-month program of research to develop (1-6 months), pilot (7-12 months), and test the efficacy (13-24 months) of a novel psycho-educational web-based resource to reduce negative attitudes towards insulin among adults with non-insulin treated T2D. This protocol describes the second stage of a three-stage program of research: 1) the process of resource development, 2) a pilot study to assess the acceptability and feasibility of the intervention and the RCT protocol, and 3) a fully-powered parallel RCT to test the efficacy of the intervention.

2.2. Aim(s)

- Intervention development: to develop a novel evidence-based psycho-educational webbased resource about insulin therapy for people with non-insulin T2D with iterative and active involvement of potential end users to ensure relevance and acceptability of the intervention. (See Section 3: Intervention Development)
- Pilot Study: to conduct a pilot 2-armed RCT to examine the acceptability and the feasibility
 of study design and a novel web-based resource among adults with non-insulin-treated T2D.
 (See full protocol V2.1))

3) Randomised Controlled Trial: to conduct an individually randomised controlled trial to test

the efficacy of a novel web-based resource (intervention), compared to widely available

existing resources (control), to reduce negative attitudes toward insulin therapy, among

adults with non-insulin-treated T2D (See full protocol V2.1)).

3. PILOT STUDY

To conduct a pilot 2-armed randomised controlled trial to examine the acceptability and the

feasibility of the study design and the novel web-based resource among adults with non-insulin-

treated T2D.

3.1. Study duration

The pilot study active recruitment, participation and data collection period will be conducted within

a three-month period. Study recruitment will be open for a maximum of 2 months or until 40

consenting eligible participants have been randomised. Participation (from study entry to exit) will

be for a minimum duration of 2 weeks and a maximum of 4 weeks.

3.2. Study objectives

3.2.1. Primary objective

The primary objective of the pilot study is to assess the feasibility (via recruitment and retention

rates, and protocol compliance) of a two-armed randomised controlled trial (RCT) design using

online enrolment, participation and data collection to evaluate the efficacy of a novel psycho-

educational insulin therapy web-based resource.

3.2.2. Secondary objectives

The secondary objectives of this study are:

to determine the acceptability of the intervention content and format for people with non-

insulin-treated T2D via (1) website usage data, (2) detailed qualitative and quantitative survey

feedback from participants about their experiences of intervention to inform future

developments.

 to estimate the likely effect of the intervention, compared to the control, on change in negative insulin appraisals; knowledge about insulin; and willingness to commence insulin therapy at follow-up.

3.3. Study design

3.3.1. Type of study

The pilot study will use a double-blinded parallel group randomised controlled trial (two-arms, 1:1 ratio) design, comparing a novel psycho-educational insulin therapy web-based resource (intervention) with widely available online text-based information about insulin (control). This design will emulate the planned fully-powered RCT (Stage 3, Section 5). Outcomes will be assessed at baseline and 2-week follow-up.

3.3.2. Study setting

Participation will be completely online, using personal computers/mobile devices.

3.4. Participants and recruitment

3.4.1. Number of participants

40 eligible participants will be recruited, allowing for 50% attrition, for a minimum sample of 20 participants (40). See section 4.9.1 for details.

3.4.2. Eligibility

Potentials participants will be enrolled in the study only if they meet all of the inclusion criteria and none of the exclusion criteria.

3.4.2.1. Inclusion criteria

Each participant must meet all of the following criteria, as self-reported, to be enrolled in this study:

Aged 18 to 75 years at the time of randomisation

Self-reported diagnosis of T2D

Currently using oral hypoglycaemic agents for the treatment of T2D

 Able to read/write in English and capable of understanding the informed consent document and provide consent

Residing in Australia at the time of randomisation and throughout the study period

Access to an internet-enabled device (i.e. computer, tablet) for the duration of the study.

3.4.2.2. Exclusion criteria

Potential participants meeting any of the following criteria will be excluded from the study:

Self-reported diagnosis of diabetes other than T2D (e.g. Type 1, gestational, LADA)

Current use of an injectable diabetes medication (i.e. GLP-1 agonist, insulin) at the time of

randomisation

Prior experience of self-administered injectable treatment for any illness or condition

Unable to read/write in English

Unable to use/access internet-enabled devices (i.e. computer, tablet) during the study

period

Reports being "very willing" to initiate insulin therapy (measured using a single-item

"hypothetical willingness" questionnaire), i.e. rendering it impossible to record

improvement in this outcome measure.

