3.4.3. Recruitment and identification of potential participants

Participants will be recruited using convenience sampling through websites, e-newsletters/blogs and

social media (Twitter, Facebook) via the researchers' affiliated professional accounts (e.g. Deakin

University, ACBRD). Australian diabetes charities, organisations and associations (e.g. Diabetes

Australia, Diabetes Victoria) will be notified of, and encouraged to promote, the study through

similar online means.

A participant prize draw will be used to incentivise participation and aid recruitment. All participants who complete the follow-up survey will be entered into a prize draw to win one double-pass gold class cinema voucher.

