3.5. Trial allocation

3.5.1. Randomisation and blinding

After the baseline survey is submitted, participants will be allocated to one of two groups, on an equal allocation basis, stratified by gender. The randomisation sequence will be computer generated and the allocation fully concealed from the investigator, researcher team and participants.

Upon trial arm randomisation participants will receive an email specifying access details (including a unique log-in) to their allocated online resource about insulin therapy. Participants in both arms will be asked to explore their allocated resource within a 2-week period, and will receive one reminder email during this period encouraging them to access/log into the resource. Access to the online resource will conclude following the 2-week period, at which time participants will be requested (via email) to complete the follow-up survey.

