3.5.2. Intervention group

Intervention group participants will receive access to the novel psycho-educational website. The development process (Stage 1) of intervention content and design is described in the Stage 1 Protocol. A description of the intervention to be assessed in the Pilot Study (Stage 2) will be added to the protocol as an appendix prior to study commencement.

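### The pilot's eligibility list and online screen do not exclude people who helped develop the website in Stage 1; if any enrol, their blinding could fail and they could shift the acceptability and ITAS results

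*Protocol*

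**What the plan says.** **Eligibility is a closed list.** Under Protocol 3.4.2, people are "enrolled in the study only if they meet all of the inclusion criteria and none of the exclusion criteria". Section 3.4.2.2 opens with "Potential participants meeting any of the following criteria will be excluded from the study". Its six criteria cover other types of diabetes, current injectable use, past self-injection, English, internet access, and being very willing to start insulin. Neither this list nor the inclusion list in 3.4.2.1 mentions Stage 1.

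**Screening is automatic.** Section 3.6 decides eligibility from the online answers. The screening items in Table 1 (3.6.1) are age, gender, country, diabetes type and duration, regimen, prior self-injection and willingness. No item at any time point asks about Stage 1 or earlier sight of the website.

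**Stage 1 involves the same population.** Section 2.2 plans "iterative and active involvement of potential end users to ensure relevance and acceptability of the intervention". Section 2.1 says the resource "is designed and refined with active involvement from end users (people with T2D) to ensure content is relevant and acceptable". On the site tested in the pilot, 3.5.2 says: "The development process (Stage 1) of intervention content and design is described in the Stage 1 Protocol".

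**Recruitment is open.** Section 3.4.3 states "Participants will be recruited using convenience sampling through websites, e-newsletters/blogs and" social media, using accounts affiliated with the researchers. Diabetes organisations are also asked to promote the study.

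**Blinding.** Section 3.3.1 calls the trial double-blinded, and 3.5.1 has "the allocation fully concealed from the investigator, researcher team and participants". The control (3.5.3) is a static page of links to existing factsheets.

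**The concern.** A person with type 2 diabetes who helped shape or test the website can pass every criterion and screening item in this protocol. Section 2.1 places development in months 1 to 6 and the pilot in months 7 to 12, so that exposure would be recent.

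Three things are at stake for each such person:

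- **Blinding.** Participant blinding depends on not knowing which resource is the new one. A contributor could tell on first log-in, in either arm.
- **Acceptability.** The outcome in 3.7 is the percentage agreeing with positively worded items, compared between arms. In the intervention arm a contributor would be rating a site they helped shape.
- **Effect estimate.** Baseline ITAS would be measured after the person had already met the intervention content, so change from baseline would not start from an unexposed state.

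The protocol already applies similar reasoning elsewhere: 3.4.2.2 excludes very willing people because improvement could not be recorded for them. Table 1 collects nothing that would let the analyst identify contributors afterwards.

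**Working it through.** **The plan's own figure.** Section 3.9.1 enrols 40 so that 20 (10 per arm) remain after 50% attrition: 20 / (1 − 0.5) = 40. This reproduces and is not in dispute.

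**Inputs.** Completers per arm: 10 (the minimum in 3.9.1) to 20 (no attrition). The rating items go only to people who report having accessed the resource (Table 1), so raters may be fewer than completers. The documents do not give the number of contributors who enrol, the true agreement rate or how contributors would rate the site. The values below for these are assumptions.

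**1. Chance that a contributor lands in a given arm.** With m contributors among 40, split 20/20 and ignoring the gender stratification, the chance that at least one falls in the intervention arm is 1 − C(40−m, 20)/C(40, 20). By symmetry the same holds for control.

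| m | Chance |
|---|---|
| 1 | 0.500 |
| 2 | 0.756 |
| 3 | 0.885 |

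**2. Acceptability.** Let n be the raters in the intervention arm, k of them contributors who always agree, and p the agreement rate among the rest. Observed agreement is (k + (n − k)p)/n, so the shift is k(1 − p)/n.

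| p | n | Shift for k = 1 (points) | Shift for k = 2 (points) |
|---|---|---|---|
| 0.60 | 10 | 4 | 8 |
| 0.60 | 20 | 2 | 4 |
| 0.80 | 10 | 2 | 4 |
| 0.80 | 20 | 1 | 2 |

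For example, with p = 0.60, n = 10 and k = 2: (2 + 8 × 0.60)/10 = 0.68, against a true 0.60.

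**3. ITAS Negative contrast, intervention arm.** Section 3.7 uses mean change from baseline to follow-up. Suppose the true effect is δ and a contributor, already exposed, shows no further change. With 10 completers the arm's mean effect becomes (9δ + 0)/10 = 0.9δ, a dilution of 10% for that person. Among 20 completers it is 1/20 = 5%. Partial further change gives less.

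**4. ITAS Negative contrast, control arm.** A contributor in control carries any Stage 1 effect in the baseline score and so changes little afterwards, like other controls. On the change score the dilution is about zero. In the ANCOVA of 3.9.2, with baseline slope b, a contributor whose baseline and follow-up are both shifted by δ moves the adjusted score by (1 − b)δ. That is a dilution of (1 − b) × 10% per person among 10. The corresponding intervention-arm figure is b × 10%. The documents do not give b; for b between 0 and 1 neither exceeds 10%.

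**The case against.** The strongest objection is that the problem depends on facts not in this document. The Stage 1 protocol is not shown. It may limit contributors to a handful or tell them not to join later stages. That contributors follow the group's channels is also unstated, and 3.4.3 recruits through national and state organisations too. The very-willing and prior-injection exclusions may remove some contributors. All of this stands and makes every consequence conditional. It does not close the gap, because eligibility for this pilot is fixed here and nothing in the criteria or screen covers the point.

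A reader might infer stronger things that the documents do not support:

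- **That the trial's blinding breaks.** It could fail for the individual contributor. Nothing shows that it fails for anyone else.
- **That each pre-exposed control among ten dilutes the effect by about 10%, and two by 20%.** That would require the person to show the full intervention effect after baseline. Stage 1 exposure comes before baseline, so the figure does not fit a change score or a baseline-adjusted analysis.
- **That ratings are certain to be inflated.** Upward bias is plausible, but nothing in the documents shows how contributors would rate the site.
- **That the Stop/Go decision is compromised.** Section 4.3 puts a summary of preliminary analyses and the recommendation in the same report. It does not say that acceptability or ITAS results decide it.

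The ITAS estimate is also labelled crude, with no significance level set (3.7, 3.9.2), and the primary objective is feasibility (3.2.1).

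**Conclusion.** The point holds as a conditional one of modest weight. As written, Stage 1 contributors with type 2 diabetes who meet the other criteria are eligible, and the data listed in Table 1 would not identify them afterwards.

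If any enrol, participant blinding could fail for them. Under 60% true agreement and contributors who always agree, each one in the intervention arm raises the acceptability percentage by about 4 points with 10 raters, or 2 with 20. Each intervention-arm contributor may dilute the ITAS contrast by up to about 10% among 10 completers, assuming no further change after baseline. The number who would enrol is unknown, and if it is none the effect is zero. Only the secondary objectives are touched; no effect on recruitment, compliance, retention or data completeness has been shown.

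**What to change.** Add one line to 3.4.2.2, such as *Took part in Stage 1 development or user testing of the study website*, and one matching yes/no item to the online eligibility screen and Table 1.

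If exclusion is not wanted, record Stage 1 involvement at baseline and report the acceptability and ITAS results with and without those people. This keeps them in the trial and makes any influence visible, but does not restore their blinding.

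The cost is one question and, under exclusion, the loss of a few otherwise eligible people. The target of 40 is unchanged, because 3.6.2.1 continues recruitment until 40 have been allocated. As 3.3.1 says the pilot is to emulate the full trial, the same line should be considered there.
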